6.2.1.2.1 Rules for DLT Evaluation

The DLT evaluation period is 35 days from the initial administration of talimogene laherparepvec. For a subject to be considered DLT-evaluable, subjects must receive 2 doses of talimogene laherparepvec (one dose of up to 4.0 mL of 10^6 PFU/mL followed by a dose of up to 4.0 mL of 10^8 PFU/mL for Dose Level 1, or 2 doses of up to 4.0 mL of 10^6 PFU/mL for Dose Level -1) during the 35 day DLT evaluation period, with the exception when a DLT occurs after the first dose. Subjects may be replaced in a cohort if they are not evaluable for DLT (ie, a subject did not receive at least 2 treatments of talimogene laherparepvec, or ended the study treatment before completion of DLT evaluation period for a reason other than experiencing a DLT).

A DLRT will review the safety data to evaluate possible drug effects and DLT. The DLRT will review the safety data of the first 3 DLT-evaluable subjects in the older age cohort (A1 or A2) to decide if the younger age cohort can be opened for enrollment. The decision to open the younger age cohort for subject enrollment will be based on < 33% DLT rate of the first 3 DLT-evaluable subjects in the older age cohort (A1 or A2) during the DLT evaluation period.

If a DLT occurs in the first 3 DLT-evaluable subjects in the older age cohort (A1 or A2), the younger age cohort will not open until a DLT rate < 33% is observed with at least 6 DLT-evaluable subjects in the older age cohort (A1 or A2). The starting dose for the younger age cohort will be Dose Level 1 (if the DLT rate in the older age cohort at Dose Level 1 is < 33%) or Dose Level -1 (if Dose Level 1 is intolerable for the older age cohort). After both cohorts are open, the DLRT will review the safety data after the earlier of the following events: (a) the addition of 3 new DLT-evaluable subjects in a cohort **until there're 9 DLT-evaluable subjects in the cohort**; (b) a DLT rate \geq 33% considering all DLT-evaluable subjects in a cohort; (c) at the occurrence of the first DLT in either cohort. **If deemed necessary, ad-hoc meetings to review the safety data can be convened anytime by the DLRT.**

After an age cohort is closed for further enrollment, the dose will be declared safe for the cohort if the DLT rate at the dose level is < 33% (**minimum of 6 DLT-evaluable subjects**). If a DLT rate \geq 33% is observed at any time in a cohort or if it is deemed **unsafe** by the DLRT to continue **enrollment** in the cohort, the dose will be declared intolerable for the cohort. If permissible based on the incidence of DLTs, enrollment will

stop when 18 **dosed** subjects **evaluable for the primary analysis** have been confirmed across cohorts A1 and B1 except in the case of dose de-escalation when 6 additional DLT-evaluable subjects at Dose Level -1 will be needed (permissible based on the incidence of DLTs). Enrollment will not be halted while the DLT-evaluation period is still ongoing. During this time, investigators should contact the medical monitor to discuss the screening and enrollment of any potential subjects. However, enrollment may be halted for the following:

- if a DLT occurs in the older age cohort while both cohorts are enrolling subjects and before the younger age cohort reaches the first safety review, then further enrollment will be halted in the younger age cohort until a DLT rate < 33% is observed with at least 6 DLT-evaluable subjects in the older age cohort;
- if dose de-escalation occurs in any cohort while both cohorts are enrolling subjects.

The DLRT will consider the totality of available data across all cohorts in coming to any recommendation, including dose de-escalation, enrollment halt, opening or re-opening of cohort(s) for enrollment and/or the starting dose for the cohorts.

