6.2.1.3 Dosage Adjustments, Delays, Rules for Withholding or Restarting, Permanent Discontinuation

Talimogene laherparepvec treatment should be continued based on the potential benefit/risk assessment of the subject.

Dose reduction within a cohort for an individual subject who experience adverse events is not allowed. If in the course of administration of talimogene laherparepvec the subject cannot tolerate the full dose due to an injection-related adverse event, the total volume given should be recorded, and the reason for intolerance should be documented as an adverse event.

If a subject experiences any of the following treatment-related toxicities, administration should be delayed until the toxicity has resolved to at least CTCAE grade 1 or baseline:

- grade 2 or greater immune-mediated adverse events, with the exception of vitiligo
- grade 2 or greater allergic reactions
- any other grade 3 or greater hematologic or non-hematologic toxicity

If the subject requires corticosteroid dosing greater than that required for maintenance physiologic replacement therapy, talimogene laherparepvec dosing should be withheld.

If a subject demonstrates evidence of new or worsening CNS metastases, all study treatments should be withheld. Resumption of talimogene laherparepvec dosing should be left to the discretion of the investigator and discussed with the Amgen medical monitor.

If talimogene laherparepvec treatment is delayed by > 1 week, that dose will be deemed to have been missed and the subject will proceed to the next scheduled treatment visit.

If talimogene laherparepvec dosing is delayed by more than 6 weeks from the date of the planned dose due to the occurrence of an adverse event that is considered related to talimogene laherparepvec, the subject must be permanently withdrawn from talimogene laherparepvec treatment. If talimogene laherparepvec dosing is delayed by more than 6 weeks from the date of the planned dose for reasons other than treatment-related toxicity, the case must be reviewed by the Amgen medical monitor in conjunction with the investigator to determine if the subject can resume talimogene laherparepvec therapy. Reason for dose change of talimogene laherparepvec is to be recorded on CRF.

Talimogene laherparepvec will be permanently discontinued for subjects meeting any of the following criteria:

- Subject developed DLT during the DLT evaluation period.

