10.1.1.4 Exploratory Endpoints

10.1.2 Analysis Sets

10.1.2.1 DLT Analysis Set

The DLT analysis set will include DLT-evaluable subjects defined as subjects who had the opportunity to be followed for at least 35 days on treatment from the initial dosing and received at least 2 treatments of talimogene laherparepvec (except subjects who had a DLT after the first dose). Subjects may be replaced in a cohort if they are not evaluable for DLT (eg, a subject did not receive study treatment, or ended the study treatment before completion of DLT evaluation period for a reason other than experiencing a DLT).

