### **7.1 DLT Analysis Set**

**The DLT analysis set will include DLT evaluable subjects defined as subjects who had the opportunity to be followed for at least 35 days from the initial dosing of talimogene laherparepvec and received at least two treatments of talimogene laherparepvec (except subjects who had a DLT after the first dose). Subjects may be replaced in a cohort if they are not evaluable for DLT (eg, a subject did not receive study treatment, or ended the study treatment before completion of DLT evaluation period for a reason other than experiencing a DLT).**

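### A DLT-free subject whose second dose is late counts as fully evaluable, with no minimum observation after that dose

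*Protocol*

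**What the plan says.** - **Period.** Protocol 6.2.1.2.1: "The DLT evaluation period is 35 days from the initial administration of talimogene laherparepvec".
- **Evaluability.** The same section requires two doses "during the 35 day DLT evaluation period, with the exception when a DLT occurs after the first dose". Replacement is optional. It covers subjects with fewer than two treatments and those who "ended the study treatment before completion of DLT evaluation period for a reason other than experiencing a DLT". A late second dose is not mentioned.
- **Analysis set.** Protocol 10.1.2.1 takes subjects who "had the opportunity to be followed for at least 35 days on treatment from the initial dosing" and had at least two treatments. SAP 7.1 takes those who "had the opportunity to be followed for at least 35 days from the initial dosing of talimogene laherparepvec and received at least two treatments". Neither says that the second treatment must fall inside the 35 days, although SAP 11 gives consistency with Protocol 6.2.1.2.1 as the reason for its rewording.
- **Timing of dose 2.** Protocol 6.2.1.1 plans it for Day 22, with at most three days' slack, and also lets the interval lengthen for toxicity. Protocol 6.2.1.3 adds: "If talimogene laherparepvec treatment is delayed by > 1 week, that dose will be deemed to have been missed". The subject then moves to the next scheduled visit, Day 36 in Protocol Table 3.
- **Primary analysis.** Protocol 10.3.3 and SAP 8.1 place it 35 days after the last subject has enrolled and had at least one dose.

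**The concern.** Protocol Table 1 shows that Dose Levels 1 and -1 share the first dose (10^6 PFU/mL) and differ only from the second dose on. What tests Dose Level 1 is therefore the observation after the first 10^8 PFU/mL injection. The evaluability rule fixes the total time from dose 1 and leaves the time after dose 2 as whatever remains.

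If dose 2 is late and no DLT is recorded by the end of the period, the subject enters the denominator with the same weight as one observed for two weeks after dose 2. The error goes in one direction, toward a lower DLT rate. That rate is the primary endpoint. It also decides whether the 2 to < 12 years cohort opens, whether the dose is de-escalated and whether a dose is declared safe, all on small numbers.

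**Working it through.** **1. The plan's own figure.** A dose is safe below 33%, so at most 1 of 6. With X the number of DLTs in six fully observed subjects, P(X ≤ 1) = (1−p)^6 + 6p(1−p)^5. For p = 10%, 20%, 30%, 40% and 50% this gives 0.886, 0.655, 0.420, 0.233 and 0.109. Protocol Table 5 and SAP Table 2 print 89%, 66%, 42%, 23% and 11%, so they are reproduced. They assume that every DLT in the six is seen.

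**2. Days left after dose 2.** Days left = 35 − (study day of dose 2 − 1).

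| Dose 2 on | How reached | Days left | If the period ends on study day 35 |
|---|---|---|---|
| Day 22 | planned | 14 | 13 |
| Day 25 | planned, +3 days | 11 | 10 |
| Day 29 | 22 + 7 | 7 | 6 |
| Day 32 | 25 + 7 | 4 | 3 |
| Day 33 | next visit, 36 − 3 | 3 | 2 |
| Day 36 | next visit | 0 | outside the period |

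Day 29 follows directly from the one-week tolerance. Day 32 requires counting the week from the end of the +3 window. Days 33 to 36 require dose 2 to be deemed missed and the first 10^8 dose given at the next visit.

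**3. Can a delayed subject still be DLT-free?** Protocol 6.2.1.3 calls for a delay for related immune-mediated events (vitiligo excepted) and allergic reactions from grade 2, and for any other related toxicity from grade 3. Protocol 6.2.1.2.3 lists no grade 2 event as such and exempts grade 3 fatigue. Its specific hematologic criteria are febrile neutropenia and low platelets with bleeding. Some toxicity delays are therefore not DLTs, and delays for other reasons never are.

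**4. Criteria with a duration.** The laboratory criterion has a limb that needs persistence beyond one week, and grade 3 non-hematologic toxicity must last more than three days. If persistence must be completed within the period, an event starting after dose 2 cannot meet the first with 7 days or fewer left, nor the second with 3 or fewer.

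**5. Illustration.** The documents give no timing of DLT risk. Assume that a share s of the risk p follows dose 2, uniformly over 14 days, and let o be the days observed after dose 2. A late subject's observable risk is q = p[(1−s) + s·o/14]. With the other five fully observed,

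P(safe) = (1−q)[(1−p)^5 + 5p(1−p)^4] + q(1−p)^5.

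At p = 0.30 the bracket is 0.168 + 0.360 = 0.528.
- s = 0.5, o = 7: q = 0.225, so P(safe) = 0.775 × 0.528 + 0.225 × 0.168 = 0.447.
- s = 1, o = 0: q = 0, so P(safe) = 0.528.

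For s from 0.5 to 1 and o from 7 to 0:

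| Quantity | All fully observed | One late | Two late |
|---|---|---|---|
| P(safe), 6 subjects, p = 30% | 42% | 45%-53% | 48%-65% |
| P(safe), 6 subjects, p = 50% | 11% | 13%-19% | 15%-31% |
| P(0 of first 3), p = 30% | 34% | 38%-49% | not computed |
| P(0 of first 3), p = 50% | 12.5% | 16%-25% | not computed |

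The last two rows use (1−p)²(1−q), for example 0.49 × 0.775 = 0.38.

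**The case against.** The case on the other side is substantial.

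- **The schedule largely protects the trial.** A second dose on Day 22 to 25 leaves 11 to 14 days, and Protocol 6.2.1.1 asks that it not be later. This stands, and it confines the point to late doses. It does not remove the point: the same section allows longer intervals for toxicity, and no evaluability rule excludes a subject dosed late.
- **A toxicity delay is often itself a DLT.** Related grade 4 non-hematologic toxicity, and grade 3 lasting beyond three days (fatigue excepted), go into the numerator and end treatment. This also stands. A reader might infer that subjects delayed for toxicity generally enter as DLT-free, but the DLT definition does not support that.
- **The shortest windows depend on the reading.** If the period closes on study day 35, a Day 36 dose is outside it and the subject is not evaluable under Protocol 6.2.1.2.1. Day 29 is the firm case.
- **The 1 of 6 versus 2 of 6 threshold has limited reach.** Cohort A1 needs at least 9 evaluable subjects. At Dose Level -1 both doses are 10^6, so the argument about an unobserved 10^8 dose does not apply. The six-subject illustration bears mainly on B1, and on opening B1 after a DLT in A1.
- **There are safeguards.** The dose level review team weighs all available data, may meet ad hoc and may stop a cohort below 33%. Adverse events are collected to 30 (+7) days after the last dose. These soften the gap but do not alter the DLT analysis set or the incidence computed from it.

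**Conclusion.** The gap is real but narrow. For a second dose later than Day 25, the plan counts a DLT-free subject as evaluable without requiring any observation after that dose: 7 days on the firm reading, 4 to 0 on wider ones. Any resulting bias is downward, toward declaring the dose safe.

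Its size cannot be stated from the documents, because they give neither the frequency of late second doses nor the timing of DLT risk. The step-5 figures show what one or two such subjects could do if risk after dose 2 is uniform over 14 days and at least half of all DLT risk follows dose 2. The lower end is a shift of about three percentage points.

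Two stronger readings are tempting. One is that the DLT rate is biased for the cohort as a whole; on-schedule subjects give no support for that. The other is that Table 5 is wrong; its arithmetic is right, and only its assumption of complete ascertainment is at issue. SAP 7.1 read alone would also admit a second dose given after the period. SAP 11 shows that this was not intended, but the wording does not exclude it.

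**What to change.** In Protocol 6.2.1.2.1, Protocol 10.1.2.1 and SAP 7.1:

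1. Count a DLT-free subject as evaluable only if followed for 35 days from the first dose and for at least the post-dose-2 observation that the Day 22 to 25 window already gives. That is 11 days. The sponsor may justify up to 14, but with 14 (± 3) day dosing a third dose can come as early as 14 − 3 = 11 days after the second, so a longer span can overlap it.
2. Count DLTs through that date. Treat a DLT-free subject not followed to it as not evaluable and replaceable.
3. Restore in SAP 7.1 the requirement that both doses fall within the 35-day period, and state which study day closes it.
4. Align the primary analysis date (Protocol 10.3.3, SAP 8.1) and the primary completion date (Protocol 3.5.2), so that a late second dose in the last subject is not cut short.

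Protocol 6.2.1.1 and 6.2.1.3 should be reconciled with this definition. The dosing and delay rules themselves need not change.

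The cost is wording plus some waiting. With an 11-day minimum, follow-up ends at Day 29 + 11 = 40, Day 32 + 11 = 43 or Day 36 + 11 = 47, against Day 36 now. Dose level review therefore waits 4, 7 or 11 days for that subject (up to 14 with the longer span), or the subject is replaced. On-schedule subjects are unaffected, since Day 25 + 11 = Day 36.

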3.4 Replacement of Subjects

Subjects enrolled may be replaced in a cohort if they are not evaluable for DLT (eg, a subject did not receive study treatment, or ended the study treatment before completion of DLT evaluation period for a reason other than experiencing a DLT). The decision to replace subjects will depend on the totality of reasons for subjects not completing the DLT evaluation.

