6.2.1.2.3 Definition of DLT

All toxicities will be graded using the CTCAE version 4.0 ([Appendix A](#)).

The occurrence of any of the following toxicities during the DLT evaluation period will be considered a DLT, if judged by the investigator to be related to the administration of talimogene laherparepvec:

- Grade 4 non-hematologic toxicity
- Grade 3 non-hematologic toxicity lasting > 3 days despite optimal supportive care
 - grade 3 fatigue will not be classified as DLT, irrespective of duration
- Any grade 3 or higher non-hematologic laboratory value if:
 - medical intervention is required, or
 - the abnormality leads to hospitalization, or

- the abnormality persists for > 1 week unless deemed not clinically important per both investigator and sponsor.
- Febrile neutropenia grade 3 or grade 4
- Thrombocytopenia < 25 x 10⁹/L associated with bleeding event requiring intervention
- Serious herpetic event:
 - herpetic encephalitis or disseminated herpetic infection
- Grade 5 toxicity (ie, death)
- Any other intolerable toxicity leading to permanent discontinuation of talimogene laherparepvec

If a subject experiences a DLT during the DLT evaluation period, study treatments will be discontinued for that subject.

Subjects who are in CR and no longer have injectable lesions will enter the 30-day safety follow-up and continue to have tumor assessments every 12 weeks for up to 24 months. Subjects who develop a new injectable lesion(s) within 12 months from the start date of treatment, but after all other injectable lesions have responded such that they are no longer injectable are eligible to restart treatment with talimogene laherparepvec under this protocol for up to a further 12 months. This includes subjects that achieve a CR and then develop a new injectable lesion.

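### The primary DLT rate does not register treatment-related toxicity that keeps a subject from dose 2 without meeting a DLT criterion, so it can understate intolerability

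*Protocol*

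**What the plan says.** **Evaluability.** Protocol 6.2.1.2.1 states: "For a subject to be considered DLT-evaluable, subjects must receive 2 doses of talimogene laherparepvec", inside the 35-day period, "with the exception when a DLT occurs after the first dose". It has no exception for a related toxicity that stops dose 2 but is not a DLT. The replacement sentence ("Subjects may be replaced in a cohort if they are not evaluable for DLT (ie, a subject did not receive at least 2 treatments") does not depend on why dose 2 was not given. Section 3.4 adds discretion: "The decision to replace subjects will depend on the totality of reasons for subjects not completing the DLT evaluation".

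**Analysis set.** Protocol 10.1.2.1 and SAP 7.1 ask for the opportunity of 35 days' follow-up and two treatments; SAP 7.1 has "received at least two treatments of talimogene laherparepvec (except subjects who had a DLT after the first dose". Neither says that the second treatment must fall inside the 35 days. SAP 11 nevertheless gives consistency with protocol 6.2.1.2.1 as the reason for its revised definition.

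**Delays.** Protocol 6.2.1.3 holds dosing for related immune-mediated events (other than vitiligo) or allergic reactions from grade 2, and for any other related toxicity from grade 3. It adds: "If talimogene laherparepvec treatment is delayed by > 1 week, that dose will be deemed to have been missed". In the Schedule of Assessments dose 2 is on Day 22 and the next injection on Day 36.

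**DLT definition.** Protocol 6.2.1.2.3 excludes one event outright: "grade 3 fatigue will not be classified as DLT, irrespective of duration". Its hematologic criteria are febrile neutropenia and low platelets with bleeding that needs intervention. There is a catch-all: "Any other intolerable toxicity leading to permanent discontinuation of talimogene laherparepvec".

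**Decision.** Protocol 6.2.1.2.1 and 10.2 declare a dose safe when fewer than 33% of DLT-evaluable subjects, with at least 6 of them, have a DLT.

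**The concern.** The primary objective is safety and tolerability, measured by DLTs. A subject with, for example, grade 3 fatigue, a grade 2 immune-mediated event, or grade 3 to 4 cytopenia without fever or bleeding may be unable to take dose 2 on schedule because of the drug. That is a tolerability failure, yet it cannot enter the DLT numerator. Depending on which definition is applied, the subject also leaves the denominator or dilutes it.

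Cohorts are small, so one or two such subjects matter. The same evaluable-only count decides whether children aged 2 to under 12 may be enrolled: no DLT among the first 3 evaluable older subjects opens the younger cohort. A replaced subject would not be visible to that count.

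**Working it through.** **1. Does the route exist?** Dose 2 is planned for Day 22. A related non-DLT event that delays it by more than a week makes it missed, and the next injection is Day 36 ± 3 days, that is Day 33 to Day 39. The 35-day period ends on Day 35 if Day 1 is counted as the first day, or on Day 36 by the protocol's convention that 21 days after dose 1 is Day 22. The replacement injection may therefore fall inside, on the edge of, or beyond the period. If beyond, the subject is non-evaluable under 6.2.1.2.1. The mandatory withdrawal rule for a related delay acts only after six weeks, about Day 22 + 42 = Day 64, whereas the primary analysis is set 35 days after the last subject's first dose.

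**2. The plan's own figures.** With 6 evaluable subjects, safe means 0 or 1 DLT, since 2/6 = 33.3%. P(safe) = (1 − x)^6 + 6x(1 − x)^5. At x = 10, 20, 30, 40 and 50% this gives 88.6, 65.5, 42.0, 23.3 and 10.9%, against 89, 66, 42, 23 and 11% in protocol Table 5. The table is reproduced.

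**3. Direction.** Let p be the probability of a DLT and q the probability that a non-DLT toxicity keeps the subject from dose 2 in the period. The expected rate is:
- p/(1 − q) if such subjects are dropped and replaced;
- p if they are kept as non-DLTs;
- p + q if they are counted as events.

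Dropping never gives less than p. It gives less than p + q whenever q > 0 and p + q < 1.

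**4. Worked counts.** With 8 dosed, 1 DLT and 2 blocked: dropped and replaced, 1/6 = 16.7% (below 33%); kept, which requires that both had a late dose 2, 1/8 = 12.5% (below 33%); counted, (1 + 2)/8 = 37.5% (not below 33%). With one blocked subject beside 1 DLT in 6, counting gives 2/7 = 28.6%, still below 33%. From 2 DLTs in 9 (22.2%), one blocked subject gives 3/10 = 30.0% and two give 4/11 = 36.4%.

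**5. Operating characteristics.** p = 20% and the values of q are assumptions; the documents give no figure. Each rate is put through the rule in step 2. For nine subjects, safe means at most 2 DLTs: P = (1 − x)^9 + 9x(1 − x)^8 + 36x²(1 − x)^7.

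| q | Rate, evaluable only | Rate, composite | P(< 33%), n = 6: evaluable / composite | P(< 33%), n = 9: evaluable / composite |
|---|---|---|---|---|
| 0% | 20.0% | 20% | 66% / 66% | 74% / 74% |
| 5% | 21.1% | 25% | 63% / 53% | 71% / 60% |
| 10% | 22.2% | 30% | 60% / 42% | 68% / 46% |
| 20% | 25.0% | 40% | 53% / 23% | 60% / 23% |

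Kept as non-DLTs, the rate is 20% and P(< 33%) with n = 6 is 66% at every q.

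**6. If blocked subjects differ in DLT risk.** Assume 20% risk in the others and 20% blocked. The measured rate is 20%. Had the blocked subjects been dosed, with risk r, the rate over everyone would be 0.8 × 20% + 0.2 × r: 24, 28 or 32% at r = 40, 60 or 80%. P(< 33%) with n = 6 would then be 55.8, 46.4 or 37.8%, against 65.5% measured. At r = 10% it would be 18%, so the measured rate would overstate.

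**The case against.** A reader might infer that excluding these subjects makes poor tolerability lower the measured DLT rate. The documents do not support that. The excluded subjects have no DLT, so the numerator is unchanged; a 20% rate becomes 22.2%, and P(declared safe) with six falls from 65.5% to 60.1%. The rate is lower only against a count that treats these events as failures, or if blocked subjects carry above-average DLT risk, which nothing in the documents quantifies. Nor are they always excluded from the analysis, because SAP 7.1 can keep a subject whose dose 2 came late.

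The other objections have weight:
- **The route is narrow.** Related grade 3 non-hematologic toxicity beyond 3 days despite supportive care is a DLT, fatigue apart. Permanent discontinuation for related intolerable toxicity is a DLT, and 6.2.1.3 lets the investigator judge in advance that a delay would exceed six weeks. In the adult pivotal study (protocol 2.2.2) the only grade 3 or 4 event in at least 2% was cellulitis, at 2.1%. That says nothing about grade 2 immune-mediated or allergic events.
- **The composite is not the endpoint.** The 33% threshold was set for DLTs; applying it to the composite is illustrative.
- **The subjects are not hidden.** The DLRT weighs all data, may meet ad hoc and may call a dose intolerable whatever the rate. Replacement is discretionary. The safety set keeps every dosed subject, SAP 10.6.2 tabulates related events and SAP 10.6.8 tabulates reasons for delay.

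All of this limits the size of the problem. It does not remove it: section 3.4 governs replacement and not the analysis set, DLRT judgement is discretionary, and no planned output sets these subjects beside the 33% rule.

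**Conclusion.** The point holds as a limitation of the primary measure. Related toxicity that keeps a subject from dose 2 within the period, without being a DLT, is uncounted whether the subject is dropped (6.2.1.2.1) or kept (10.1.2.1, SAP 7.1). The DLT rate can therefore understate intolerability.

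The size depends on the blocked fraction. Under the assumed 20% DLT rate, the gap in P(< 33%) with six subjects is about 10, 18 and 30 percentage points at 5, 10 and 20% blocked, and zero if none are blocked. In counts, it takes two blocked subjects to carry 1/6 or 2/9 across the line. There is also a plain inconsistency over whether dose 2 must fall inside the 35 days, although SAP 11 claims consistency. This is a worthwhile, inexpensive improvement to reporting. It does not show that the DLT definition, the threshold or the dosing rules are wrong.

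**What to change.** 1. In SAP 10.6.1 pre-specify a supportive rate with exact 95% CI. The numerator is DLTs plus dosed subjects who did not receive dose 2 within the 35-day period because of treatment-related toxicity. The denominator is the DLT analysis set plus any such subjects not already in it.
2. In protocol 10.3.2 provide that rate to the DLRT at each review, before any such subject is replaced, with a listing of every non-evaluable dosed subject and the reason.
3. Report it beside the primary DLT rate wherever a dose is declared safe.
4. Reconcile protocol 6.2.1.2.1 with protocol 10.1.2.1 and SAP 7.1 and 11 on whether dose 2 must fall within the 35 days.

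The DLT definition, the 33% rule and the dosing rules stay unchanged. The cost is one table row and one DLRT listing; reasons for delay are already due to be tabulated under SAP 10.6.8. The downside is a supportive figure that may look less favourable than the primary one.
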